### **Electrocardiogram**

Descriptive statistics (n, mean, SE, SD, 95% CI, minimum, median, and maximum) for actual values and changes from baseline will be tabulated for the parameters listed below at each scheduled time point, by study treatment.

The ECG variables that will be analyzed are heart rate, PR interval, QRS interval, QT interval, and corrected QT (QTc) interval using the following correction methods: QT corrected according to Bazett's formula, QTcF.

All clinically relevant abnormalities in ECG waveform that are changes from the baseline readings will be reported (eg, changes in T-wave morphology or the occurrence of U-waves).

The abnormalities in ECG parameters will be determined according to the criteria specified in the Cardiovascular Safety – Abnormalities Table ([Attachment 2](#)).

The percentage of subjects who experience (worst) abnormalities in ECG parameters will be tabulated by study treatment.

### **Vital Signs**

Descriptive statistics (n, mean, SE, SD, 95% CI, median, minimum, and maximum) for the actual values and changes from baseline per time point will be tabulated for analysis for the following variables, by study treatment: supine SBP, DBP, and pulse rate, and body temperature.

The abnormalities in vital signs will be determined according to the criteria specified in the Cardiovascular Safety – Abnormalities Table ([Attachment 2](#)).

The percentage of the subjects who experience (worst) abnormalities in vital signs will be tabulated by study treatment.

### **Physical Examination**

Physical examination results and abnormalities will be listed.

## **11.11. Interim Analyses**

At the Week 12 interim analyses, the sponsor study team will remain blinded to the randomization codes (unless the DRC recommends unblinded analyses, see below) and data will be analyzed using dummy identification and aggregated efficacy summary statistics. At the unblinded Week 24 interim analyses (and subsequent analyses), the sponsor study team members involved in safety monitoring of the treatment extension phase as well as the investigator, site personnel and subjects will remain blinded. The sponsor study team members involved in safety monitoring of the treatment extension phase will remain blinded to the treatment/randomization codes until the end of the treatment extension phase while the investigator, site personnel and

subjects will remain blinded until the end of the study. Note that blinding does not apply to the JNJ-56136379 monotherapy arms.

Interim analyses, encompassing efficacy, safety, and pharmacokinetics, may be conducted for **Part A** and **Part B** at study Week 12, 24, 36, 48 and 72 separately when at least 80% of subjects have completed the respective visit (ie, Week 12, Week 24 for all subjects, FU Week 12/Week 36 and FU Week 24/Week 48 for subjects receiving 24/48 weeks of study treatment, and, FU Week 24 for subjects receiving 48 weeks of study treatment, respectively) or have discontinued earlier (see also [Figure 1](#)).

At the sponsor's discretion, these interim analyses may also be performed separately by subject population (currently not being treated versus virologically suppressed) in case recruitment rates differ between the subject populations.

Additional interim analyses may be performed at the sponsor's discretion to support decision making for further development of JNJ-56136379 and to support interactions with health authorities.

A final analysis will be performed when all subjects in the study have completed the last study-related follow-up visit or have discontinued earlier.

## **11.12. Data Review Committee**

A DRC, comprised of sponsor personnel outside of the sponsor study team responsible for managing the study, supplemented with an external certified hepatologist, will be established. The DRC will monitor efficacy and safety data in an unblinded manner during study conduct on a regular basis and/or ad hoc in case of emergent safety signals identified through medical monitoring. The DRC will also review interim data and formulate recommended decisions/actions in accordance with the objectives of the interim analysis.

The DRC can also recommend to conduct an additional unblinded interim analysis. The DRC will provide instructions to the sponsor study team with respect to any changes to study conduct that it deems necessary in light of the emerging safety and efficacy data. This may include the addition, modification, or closure of treatment arms. The sponsor, in agreement with the DRC, selected the JNJ-56136379 dose for Part B based on all safety, PK, and antiviral activity data available following completion of the highest JNJ-56136379 dose group (who received 250 mg once daily) in the Phase 1 study 56136379HPB1001 in treatment-naïve CHB-infected subjects treated for 28 days.

The DRC may also endorse any sponsor recommendations for the addition of further parts to the study.

A detailed description of the roles and responsibilities of the DRC will be documented in the DRC charter.

## 12. ADVERSE EVENT REPORTING

Timely, accurate, and complete reporting and analysis of safety information from clinical studies are crucial for the protection of subjects, investigators, and the sponsor, and are mandated by regulatory agencies worldwide. The sponsor has established Standard Operating Procedures in conformity with regulatory requirements worldwide to ensure appropriate reporting of safety information; all clinical studies conducted by the sponsor or its affiliates will be conducted in accordance with those procedures.

### Method of Detecting Adverse Events and Serious Adverse Event

Care will be taken not to introduce bias when detecting AEs or SAEs. Open-ended and nonleading verbal questioning of the subject is the preferred method to inquire about AE occurrence.

#### 12.1. Definitions

##### 12.1.1. Adverse Event Definitions and Classifications

###### Adverse Event

An AE is any untoward medical occurrence in a clinical study subject administered a medicinal (investigational or non-investigational) product. An AE does not necessarily have a causal relationship with the intervention. An AE can therefore be any unfavorable and unintended sign (including an abnormal finding), symptom, or disease temporally associated with the use of a medicinal (investigational or non-investigational) product, whether or not related to that medicinal (investigational or non-investigational) product. (Definition per International Council for Harmonization [ICH])

This includes any occurrence that is new in onset or aggravated in severity or frequency from the baseline condition, or abnormal results of diagnostic procedures, including laboratory test abnormalities.

**Note:** The sponsor collects AEs starting with the signing of the ICF (refer to Section 12.3.1).

###### Serious Adverse Event

An SAE based on ICH and European Union Guidelines on Pharmacovigilance for Medicinal Products for Human Use is any untoward medical occurrence that at any dose:

- Results in death
- Is life-threatening  
(The subject was at risk of death at the time of the event. It does not refer to an event that hypothetically might have caused death if it were more severe.)
- Requires inpatient hospitalization or prolongation of existing hospitalization
- Results in persistent or significant disability/incapacity
- Is a congenital anomaly/birth defect

- Is a suspected transmission of any infectious agent via a medicinal product
- Is Medically Important\*

\*Medical and scientific judgment should be exercised in deciding whether expedited reporting is also appropriate in other situations, such as important medical events that may not be immediately life-threatening or result in death or hospitalization but may jeopardize the subject or may require intervention to prevent one of the other outcomes listed in the definition above. These should usually be considered serious.

If a serious and unexpected AE occurs for which there is evidence suggesting a causal relationship between the study intervention and the event (eg, death from anaphylaxis), the event must be reported as a serious and unexpected suspected adverse reaction even if it is a component of the study endpoint (eg, all-cause mortality).

### **Unlisted (Unexpected) Adverse Event/Reference Safety Information**

An AE is considered unlisted if the nature or severity is not consistent with the applicable product reference safety information. For JNJ-56136379, the expectedness of an AE will be determined by whether or not it is listed in the IB.

### **Adverse Event Associated With the Use of the Drug**

An AE is considered associated with the use of the intervention if the attribution is possible, probable, or very likely by the definitions listed in Section [12.1.2](#).

#### **12.1.2. Attribution Definitions**

##### **Not Related**

An AE that is not related to the use of the intervention.

##### **Doubtful**

An AE for which an alternative explanation is more likely, eg, concomitant drug(s), concomitant disease(s), or the relationship in time suggests that a causal relationship is unlikely.

##### **Possible**

An AE that might be due to the use of the intervention. An alternative explanation, eg, concomitant drug(s), concomitant disease(s), is inconclusive. The relationship in time is reasonable; therefore, the causal relationship cannot be excluded.

##### **Probable**

An AE that might be due to the use of the intervention. The relationship in time is suggestive (eg, confirmed by dechallenge). An alternative explanation is less likely, eg, concomitant drug(s), concomitant disease(s).

## Very Likely

An AE that is listed as a possible adverse reaction and cannot be reasonably explained by an alternative explanation, eg, concomitant drug(s), concomitant disease(s). The relationship in time is very suggestive (eg, it is confirmed by dechallenge and rechallenge).

### 12.1.3. Severity Criteria

An assessment of severity grade will be made by the investigator using the general categorical descriptors outlined in the DAIDS Toxicity Grading Scale.

The investigator should use clinical judgment in assessing the severity of events not directly experienced by the subject (eg, laboratory abnormalities).

## 12.2. Special Reporting Situations

Safety events of interest on a sponsor study intervention that may require expedited reporting or safety evaluation include, but are not limited to:

- Overdose of a sponsor study drug.
- Suspected abuse/misuse of a sponsor study drug
- Accidental or occupational exposure to a sponsor study drug
- Medication error involving a sponsor product (with or without subject exposure to the sponsor study drug, eg, name confusion)
- Exposure to a sponsor study drug from breastfeeding

Special reporting situations should be recorded in the eCRF. Any special reporting situation that meets the criteria of an SAE should be recorded on the SAE page of the eCRF.

## 12.3. Procedures

### 12.3.1. All Adverse Events

All AEs and special reporting situations, whether serious or non-serious, will be reported from the time a signed and dated ICF is obtained until completion of the subject's last study-related procedure, which may include contact for follow-up of safety. Serious AEs, including those spontaneously reported to the investigator within 30 days after the last dose of study drug, must be reported using the SAE Form. The sponsor will evaluate any safety information that is spontaneously reported by an investigator beyond the time frame specified in the protocol.

All events that meet the definition of an SAE will be reported as SAEs, regardless of whether they are protocol-specific assessments.

All AEs, regardless of seriousness, severity, or presumed relationship to study drugs, must be recorded using medical terminology in the source document and the eCRF. Whenever possible, diagnoses should be given when signs and symptoms are due to a common etiology (eg, cough, runny nose, sneezing, sore throat, and head congestion should be reported as "upper respiratory infection"). Investigators must record in the eCRF their opinion concerning the relationship of

the AE to study therapy. All measures required for AE management must be recorded in the source document and reported according to sponsor instructions.

The sponsor assumes responsibility for appropriate reporting of AEs to the regulatory authorities. The sponsor will also report to the investigator (and the head of the investigational institute where required) all suspected unexpected serious adverse reactions (SUSARs). The investigator (or sponsor where required) must report SUSARs to the appropriate IEC/IRB that approved the protocol unless otherwise required and documented by the IEC/IRB. A SUSAR will be reported to regulatory authorities unblinded. Participating investigators and IEC/IRB will receive a blinded SUSAR summary, unless otherwise specified.

For all studies with an outpatient phase, including open-label studies, the subject must be provided with a "wallet (study) card" and instructed to carry this card with them for the duration of the study indicating the following:

- Study number
- Statement, in the local language(s), that the subject is participating in a clinical study
- Investigator's name and 24-hour contact telephone number
- Local sponsor's name and 24-hour contact telephone number (for medical staff only)
- Site number
- Subject number
- Any other information that is required to do an emergency breaking of the blind

### **12.3.2.      Serious Adverse Events**

All SAEs occurring during the study must be reported to the appropriate sponsor contact person by study-site personnel within 24 hours of their knowledge of the event.

Information regarding SAEs will be transmitted to the sponsor using the SAE Form, which must be completed and signed by a physician from the study site, and transmitted to the sponsor within 24 hours. The initial and follow-up reports of an SAE should be made by facsimile (fax).

All SAEs that have not resolved by the end of the study, or that have not resolved upon discontinuation of the subject's participation in the study, must be followed until any of the following occurs:

- The event resolves
- The event stabilizes
- The event returns to baseline, if a baseline value/status is available
- The event can be attributed to agents other than the study drugs or to factors unrelated to study conduct

- It becomes unlikely that any additional information can be obtained (subject or health care practitioner refusal to provide additional information, lost to follow-up after demonstration of due diligence with follow-up efforts)

Suspected transmission of an infectious agent by a medicinal product will be reported as an SAE. Any event requiring hospitalization (or prolongation of hospitalization) that occurs during the course of a subject's participation in a study must be reported as an SAE, except hospitalizations for the following:

- Hospitalizations not intended to treat an acute illness or AE (eg, social reasons such as pending placement in long-term care facility)
- Surgery or procedure planned before entry into the study (must be documented in the eCRF).

**Note:** Hospitalizations that were planned before the signing of the ICFs, and where the underlying condition for which the hospitalization was planned has not worsened, will not be considered SAEs. Any AE that results in a prolongation of the originally planned hospitalization is to be reported as a new SAE.

The cause of death of a subject in a study whether or not the event is expected or associated with the study intervention, is considered an SAE.

### **12.3.3. Pregnancy**

All initial reports of pregnancy in female subjects or partners of male subjects must be reported to the sponsor by the study-site personnel within 24 hours of their knowledge of the event using the appropriate pregnancy notification form. Abnormal pregnancy outcomes (eg, spontaneous abortion, fetal death, stillbirth, congenital anomalies, ectopic pregnancy) are considered SAEs and must be reported using the SAE Form. Any subject who becomes pregnant during the study must be promptly withdrawn from the study and discontinue further JNJ-56136379 treatment.

Follow-up information regarding the outcome of the pregnancy and any postnatal sequelae in the infant will be required.

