- n. PRO assessments are not needed at the early withdrawal visit if PRO was already assessed within 2 weeks prior to the early withdrawal visit.
- o. Only applicable to subjects in the pharmacokinetic subgroup and subjects enrolled at a site with an on-site Fibroscan device.
- p. If a subject discontinues study treatment before the end of the 24-week treatment phase or, if applicable, the 24-week treatment extension phase (ie, Week 48 visit), a treatment withdrawal visit should be performed after which the subject will enter the 24-week follow-up, unless the subject withdraws consent. NA treatment (either ETV or TDF as per local practice) should be continued or, in case of JNJ-56136379 monotherapy, started at the time of early discontinuation of study treatment as per local treatment guidelines. An additional 24-week follow-up (as per local treatment guidelines), by their primary care physician outside of the study, is recommended after the 24-week follow-up phase in the study, for subjects who do not continue or start NA treatment at Week 24 or 48. Subjects who withdraw consent will be offered an optional safety follow-up visit.
- q. HBcrAg and HBV RNA samples may be batched and only selected samples may be tested. Samples can be used for assessment of other serologic/virologic markers of HBV.
- r. Subjects withdrawing consent during the follow-up period will be offered an optional safety follow-up visit.
- s. For female subjects on a hormonal contraceptive regimen (regardless of type and route of administration), the start of contraceptive administration at the last initiated cycle (if applicable for the type of contraception) will be documented in the eCRF.
- t. All follow-up study visits are to be scheduled relative to the last dose of JNJ-56136379 and are to occur at the end of Weeks 2, 4, 12, and 24. The visit window is  $\pm 2$  days of the protocol-specified date at Weeks 2-4,  $\pm 5$  days of the protocol-specified date through Week 24.

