#### **9.1.5. Post-Treatment Phase (Follow-Up)**

For details on the follow-up after the last study drug intake of the study treatment phase (Week 24 or Week 48) or in case of dropout, please refer to the [TIME AND EVENTS SCHEDULE](#) for the post-treatment (follow-up) phase. All subjects who received 24 weeks of treatment, who received 48 weeks of treatment and did not meet the treatment completion criteria as described in Section 6.3, or who discontinued study treatment early (either 24 or 48 weeks of study treatment) will be followed-up for 24 weeks (Schedule 1). Subjects who meet the study completion criteria (see Section 6.3) will be followed-up for 48 weeks (Schedule 2).

If a subject withdraws from the study (ie, withdrawal of consent), the subject will be offered an optional safety follow-up visit.

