## **10.2. Discontinuation of Study Treatment/Withdrawal from the Study**

### **Discontinuation of Study Treatment**

A subject will not be automatically withdrawn from the study if he or she has to discontinue study treatment before the end of the 24- or 48 week treatment phase, as applicable.

A subject's JNJ-56136379 treatment must be discontinued and NA may be discontinued based on investigator judgement in consultation with the sponsor if:

1. The subject withdraws consent.
2. The investigator believes that for safety reasons or tolerability reasons (eg, AE) it is in the best interest of the subject to discontinue study treatment.
3. The subject becomes pregnant.
4. The subject has a  $\geq$  gradea 3 rash (see [Attachment 3](#)).
5. The subject has a  $\geq$  grade 3 allergic reaction, nausea, or diarrhea.
6. The subject has a grade 4 AE or confirmed laboratory abnormality (with the exception of ALT/AST elevations) considered at least possibly related to study drugs by the investigator.
7. The subject experiences a treatment-emergent elevation of ALT  $>2x$  baseline value, in combination with either direct bilirubin  $>1.2x$  ULN or INR  $>1.5x$  ULN or serum albumin  $<$  LLN, confirmed by retesting.
8. The subject has signs of hepatic decompensation (ie, clinical evidence of ascites, bleeding varices, or hepatic encephalopathy).
9. The subject has a confirmed  $\geq$  grade 3 serum creatinine abnormality, regardless of the relationship to the study drugs. In this case, JNJ-56136379 must be discontinued. The subject may continue ETV or switch from TDF to ETV at the investigator's discretion and enter follow-up.

Subjects who are receiving TDF and develop confirmed treatment-emergent  $\geq$  grade 3 abnormalities in urinalysis, considered at least possibly related to TDF, may switch to ETV and continue JNJ-56136379 for 4-8 weeks. If the urinalysis abnormality persists at the end of the 4-8 weeks NA switching phase, JNJ-56136379 must be discontinued. Subjects may continue NA treatment at the investigator's discretion and enter follow-up.

---

a Grades in this list are per the DAIDS Toxicity Grading Scale.

If the confirmed  $\geq$  grade 3 urinalysis abnormality is not considered at least possibly related to TDF or ETV, or any other concomitant disease and its medication, JNJ-56136379 must be discontinued. Subjects may continue NA treatment at the investigator's discretion and enter follow-up.

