### **Withdrawal From the Study**

A subject will be withdrawn from the study for any of the following reasons:

- Lost to follow-up.
- Withdrawal of consent.
- Death.

If a subject discontinues study treatment before the end of the 24-week treatment phase or the 24-week treatment extension phase, follow-up assessments should be obtained until 24 weeks after EOT (Schedule 1) unless the subject withdraws consent.

If a subject withdraws before completing the study, the reason for withdrawal is to be documented in the eCRF and in the source document. Subjects who withdraw consent will be offered an optional safety follow-up visit. Study treatment assigned to the withdrawn subject may not be assigned to another subject. Subjects who withdraw will not be replaced.

If a subject is lost to follow-up, every reasonable effort must be made by the study-site personnel to contact the subject and determine the reason for discontinuation/withdrawal. The measures taken to follow up must be documented.

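### Section 12.3.3 withdraws a pregnant subject from the study, while Section 10.2 stops JNJ-56136379 and keeps her in Schedule 1 follow-up; four scheduled visits depend on which rule a site follows

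*Protocol*

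**What the plan says.** Protocol Section 12.3.3 (Pregnancy) gives a two-part instruction: "Any subject who becomes pregnant during the study must be promptly withdrawn from the study and discontinue further JNJ-56136379 treatment". It then requires information on the outcome of the pregnancy and on the infant.

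Protocol Section 10.2 covers the same event under treatment discontinuation. It opens with "A subject will not be automatically withdrawn from the study if he or she has to discontinue study treatment" before the planned end of the treatment phase. It then lists the situations in which JNJ-56136379 "treatment must be discontinued and NA may be discontinued based on investigator judgement in consultation with the sponsor if" they occur; item 3 is "The subject becomes pregnant".

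Under its separate subheading on leaving the study, Section 10.2 says "A subject will be withdrawn from the study for any of the following reasons" and names three: loss to follow-up, withdrawal of consent and death. For anyone who stops treatment early, "follow-up assessments should be obtained until 24 weeks after EOT (Schedule 1) unless the subject withdraws consent".

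The schedules agree with Section 10.2. Footnote p of Schedule 1 says that "a treatment withdrawal visit should be performed after which the subject will enter the 24-week follow-up, unless the subject withdraws consent". Footnote kk of the treatment-phase schedule says the same in substance, and SAP Appendices 5 and 6 reproduce both footnotes.

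The optional safety visit is described in Section 9.1.5: "If a subject withdraws from the study (ie, withdrawal of consent), the subject will be offered an optional safety follow-up visit".

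**The concern.** A site with a pregnant subject cannot obey both sections. Section 12.3.3 removes her from the study, whereas Section 10.2 removes only the drug. Whichever the site follows, it departs from the other.

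What is at stake is scheduled monitoring of the mother after exposure to an investigational drug. Under 12.3.3 the planned HBV DNA, chemistry (including ALT), ECG and pharmacokinetic follow-up would end, as would study-supplied NA at FU Weeks 4 and 12. The fallback visit does not clearly reach her, because the protocol ties it to withdrawal of consent and she has not withdrawn consent. The earliest lost visits fall while the drug is still clearing.

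Section 12.3.3 is not limited to the treatment phase. A pregnancy found during follow-up would also trigger withdrawal, although only the visits still to come would be lost.

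**Working it through.** **1. The two rules side by side, for a pregnancy found on treatment**

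| | Section 12.3.3 | Section 10.2 with footnotes kk and p |
|---|---|---|
| JNJ-56136379 | Stop | Stop |
| NA | Not addressed | Investigator judgement, sponsor consulted |
| Study participation | Withdraw promptly | Not automatically withdrawn; pregnancy is not among the three listed reasons |
| Schedule 1 follow-up | Ends with withdrawal | Required to 24 weeks after end of treatment; sole exception is withdrawal of consent |
| Pregnancy and infant outcome | Required | Not addressed |

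The rows on study participation and follow-up conflict. No cross-reference or precedence statement links the sections.

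**2. Visits at stake** (counted from the Schedule 1 table, after the early treatment withdrawal visit)

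| | FU W2 | FU W4 | FU W12 | FU W24 | Total |
|---|---|---|---|---|---|
| Visit | yes | yes | yes | yes | 4 |
| HBV DNA | yes | yes | yes | yes | 4 |
| Blood chemistry | yes | yes | yes | yes | 4 |
| ECG | – | yes | yes | yes | 3 |
| Pharmacokinetics | yes | yes | – | – | 2 |

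Under Section 10.2 she is due 4 of 4 visits; under 12.3.3 she is due 0 of 4. The early treatment withdrawal visit is outside this count. In footnotes kk and p it is granted in the same sentence that sends the subject into follow-up. If 12.3.3 overrides that sentence, the visit has no clear basis either.

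**3. Drug remaining at the first lost visits**

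Input: terminal half-life of 93.3 to 116 hours in healthy subjects (Protocol Section 1.1). Fraction of the last level remaining = 0.5^(hours / half-life).

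- FU Week 2 (336 h): 0.5^(336/93.3) = 8.2%; 0.5^(336/116) = 13.4%.
- FU Week 4 (672 h): 0.5^(672/93.3) = 0.7%; 0.5^(672/116) = 1.8%.

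Section 11.4 uses these two visits to describe elimination. The calculation does not apply to the roughly 40 of 220 planned subjects on placebo+NA (10 in each of Arms 2, 4, 7 and 9), who have no JNJ-56136379 to clear.

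**4. How many subjects: an illustration**

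Assumptions: 30% to 40% of the 220 planned subjects are women of childbearing potential (not in the documents), and the failure rate is 1% per year, the ceiling in inclusion criterion 8 for consistent and correct use. Contraception is required during treatment plus 90 days.

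- Time at risk: 24 weeks + 90 days = 258 days = 0.71 years; 48 weeks + 90 days = 426 days = 1.17 years.
- Low: 220 × 0.30 × 0.71 × 0.01 = 0.47.
- High: 220 × 0.40 × 1.17 × 0.01 = 1.03.

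The result is about 0.5 to 1.0 pregnancies. Attachment 1 warns that typical-use failure rates may differ and that hormonal methods may interact with JNJ-56136379, so the true figure could be higher.

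**5. Primary endpoint**

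Both sections stop JNJ-56136379. In SAP Table 1 the treatment phase ends 5 days after the last study agent intake, and SAP Section 2.3 assigns visits within phases. Schedule 1 visits after an early stop therefore count as follow-up and would not supply her Week 24 value under either rule.

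**The case against.** The strongest reply is that the sections can be read together. Section 10.2 says subjects are not automatically withdrawn, which leaves room for exceptions, and its list of three reasons does not say it is exhaustive. Section 12.3.3 could then be a specific added reason that overrides a general rule. This softens the clash but does not remove it. Section 10.2 also names pregnancy, so it is not merely general, and its follow-up duty has one stated exception, which is not pregnancy. Nor can withdrawal in 12.3.3 mean stopping treatment only, since that sentence orders both acts.

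A second reply is that the sponsor learns of every pregnancy within 24 hours and could settle each case centrally. That stands as a practical safeguard, and it makes divergent handling between sites a possibility, not an expectation. It does not tell the sponsor which section applies.

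A third reply is that adding pregnancy to the withdrawal list in Section 10.2 would also remove the contradiction. That is true, but it would do so by giving up off-drug monitoring of an exposed subject. A related point is that Schedule 1 includes fasting chemistry and exploratory sampling not designed for pregnancy. The sponsor may wish to lighten the schedule, but that is no reason to end it.

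A reader might infer that all safety follow-up of the mother stops. The documents do not support this. Section 12.3.3 keeps pregnancy and infant outcome, and Section 12.3.2 follows unresolved serious adverse events after participation ends. Section 12.3.1 runs adverse event reporting to the last study-related procedure, which may include a safety contact. Section 9.9 follows clinically significant abnormalities that persist at early withdrawal.

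**Conclusion.** The contradiction is real, sits in current operative text, and makes the protocol wrong as written. For a pregnancy found on treatment, 4 scheduled follow-up visits and possibly the early treatment withdrawal visit depend on which section is followed. What is lost is scheduled in-study monitoring of the mother, not all care or all safety reporting.

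The number of subjects is small. A reader might take 0.5 to 1.0 pregnancies as an upper bound. It is not: it combines an assumed share of women with a perfect-use rate. At that scale the missing pharmacokinetic samples would matter little to the trial-wide summary; the concern is the individual subject. No effect on the primary endpoint is claimed. The correction should be made because it is cheap and because the affected subject is one for whom monitoring after exposure matters.

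**What to change.** In Section 12.3.3, replace the instruction to withdraw the subject and stop the drug with: *must promptly discontinue JNJ-56136379 treatment, if ongoing, and continue follow-up assessments per Section 10.2 (or the follow-up schedule already under way) unless consent is withdrawn*. Leave the sentence on pregnancy outcome and the infant unchanged.

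The cost is one sentence in the next amendment. No new procedures are needed, since Schedules 1 and 2 already exist, and the subject remains free to withdraw consent.
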